## 4.2 Study Objectives / Endpoints

Objective	Endpoint
Primary	
To demonstrate if the use of DigiVibe is superior to no intervention in reducing pain scores during intramuscular injections, subcutaneous injections, and fingersticks.	Difference between DigiVibe and no intervention on pain scores.

## 4.3 Study Population

### 4.3.1 Study Subjects and Approximate Number of Subjects

This is a single-center study which will include the participation of twenty (20) subjects.

### 4.3.2 Eligibility Criteria

#### Inclusion Criteria:

Subjects must meet each of the following inclusion criteria to be eligible for enrollment into the study:

1. Age  $\geq$  18 years
2. BMI 18.5-29.9 kg/m^2 (normal)
3. Self-reported fear/dislike of needles

#### Exclusion Criteria:

Subjects presenting with any of the following exclusion criteria will not be eligible for enrollment into the study:

1. Chronic (daily) use of nonsteroidal anti-inflammatory drugs (NSAIDs) (i.e. ibuprofen, aspirin, naproxen, etc.), antiplatelet medications (i.e. clopidogrel, prasugrel, ticagrelor, cangrelor, cilostazol, etc), or anticoagulant medications (i.e. warfarin, dabigatran, rivaroxaban, apixaban, edoxaban, heparin, enoxaparin, fondaparinux, etc.)

- Note: NSAIDs used as needed are not excluded as long as they are not used within 3 days of study screening and enrollment
- 2. Chronic (daily) use of analgesics (i.e. acetaminophen, NSAIDs [ie. ibuprofen, naproxen], opioids [ie. morphine, oxycodone, fentanyl], lidocaine, cannabinoids [ie. CBD, THC],)
  - Note: analgesics used as needed are not excluded as long as they are not used within 3 days of study screening and enrollment
- 3. Any condition in the opinion of the study investigator that would potentially confound the results of this study

#### **4.4 Study Duration**

##### **4.4.1 Approximate Duration of Subject Participation**

Subjects will actively participate in the study for up to one (1) day.

Discontinuation will be based upon investigator's clinical determination and/or by subject decision. All subjects are free to terminate their participation in the study at any time, and the details regarding discontinuation will be recorded.

##### **4.4.2 Screen Failures**

If a subject consents to participate in the clinical trial and is not enrolled, they are considered a screen failure. A subject can screen fail at any time during Visit 1 prior to initiating study procedures. The reason for the subject screen failing must be documented in the subject's source documentation.

##### **4.4.3 Premature Study Treatment Discontinuation**

If a subject decides to discontinue their study participation at any time during Visit 1 and after study procedures (post consent) have begun, the reason(s) of study discontinuation must be recorded in the subject source documentation.

If the subject discontinued study participation due to an adverse event (AE), the AE must be reported, and the subject will be followed up after discontinuation until the AE is resolved or considered medically stable by the investigator.

#### **4.4.4 Withdrawal documentation**

The subject may withdraw consent at will at any time. The subject's request to withdraw from the trial must always be respected. In case of withdrawal, the investigator will record the reason for subjects' withdrawal.

Subject participation in the study may be discontinued for reasons including, but not limited to:

- Withdrawal of subject's consent
- Subject preference
- Decision of the subject's study investigator

#### **4.4.5 Follow-up on Withdrawn Subjects**

Early discontinuation does not nullify the need to follow AEs until resolution or stabilization.

#### **4.4.6 Approximate Duration of Study**

This study is anticipated to be completed within approximately one (1) month, including subject enrollment, data collection, and analysis.

### **4.5 Study Visits**

#### Pre-screening

Potential subjects whose BMI is 18.5-29.9 kg/m^2 will be identified in the study investigator's clinic Electronic Medical Record (EMR) and contacted to determine if they have a fear/dislike of needles.

#### Visit 1 (Day1); In-Person Onsite Visit)

Subjects will be consented and assessed for eligibility to enroll in the study. Subject targeted concomitant medications and targeted medical history will be reviewed and recorded. The subjects BMI and vital signs will be obtained.

Following confirmation of eligibility, subjects will be enrolled. Subjects will first undergo two fingersticks with a 30-gauge Unistik lancing device on pulp of their middle finger. The first fingerstick will be performed with no intervention (as per standard of care).

Immediately following the fingerstick, subjects will be provided the VAS pain scale and asked to assess their level and pain and document it by circling the level of pain. After waiting 5 minutes, the DigiVibe device will be applied to the pulp of the other middle finger for 20 seconds, the lancet device will be inserted into the center of the DigiVibe device, and then the second fingerstick will be immediately performed with the DigiVibe device still vibrating through the release of the lancing device. Immediately following the fingerstick, subjects will be provided the VAS pain scale and asked to assess their level and pain and document it by circling the level of pain.

Subjects will then undergo two SC injections with a 30-gauge 4mm needle on the lower quadrant of their abdomen at least 2 inches from the belly button. The first SC injection will be performed with no intervention (as per standard of care). Immediately following the injection, subjects will be provided with the VAS pain scale and asked to assess their level and pain and document it by circling the level of pain. After waiting 5 minutes, the DigiVibe device will be applied to the other side of the abdomen on the lower quadrant for 20 seconds and then the second SC injection will be immediately performed with the DigiVibe device still vibrating the injection site during the entire injection process. Immediately following the SC injection, subjects will be provided the VAS pain scale and asked to assess their level and pain and document it by circling the level of pain.

Subjects will then undergo two IM injections. Subjects will undergo alternating assignments to either a 25-gauge 1 inch needle or a 30-gauge 1 inch needle in the upper arm deltoid muscle. The alternating assignment should be performed separately for the males and females so there is an equal distribution of males and females assigned to 25-gauge and 30-gauge. The alternating assignments must be documented. The first IM injection will be performed with no intervention (as per standard of care). Immediately following the injection, subjects will be provided with the VAS pain scale and asked to assess their level and pain and document it by circling the level of pain. After waiting 5 minutes, the DigiVibe device will be applied to the other deltoid muscle for 20 seconds and then the second IM injection will be immediately performed with the DigiVibe device still vibrating the injection site during the entire injection process. Immediately following the IM injection, subjects

will be provided the VAS pain scale and asked to assess their level and pain and document it by circling the level of pain.

Subject AEs will be recorded.

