### **4 STUDY DESIGN**

#### **4.1 Description**

This is a single-center, unblinded, prospective, cross-over study. The study population will include twenty (n=20) healthy subjects (10 men and 10 women) over the age of 18 with a self-reported fear/dislike of needles. Subjects who qualify for the study based on the study inclusion and exclusion criteria and who consent to participate in the study will undergo two (2) intramuscular (IM) injections in the deltoid muscle, two (2) subcutaneous (SC) injections in the abdomen, and two (2) fingersticks with a lancing device in the middle finger. Normal Saline (NS) will be used for the IM and SC injections. The study duration per subject is expected to be one (1) day.

While the complete mechanisms of pain and pain diversion are not completely understood, DigiVibe locally targets the skin's pain receptors. Therefore, it is proposed that the vibrations from the DigiVibe device will counteract and/or lessen the pain around the injection site. This study will determine whether the use of DigiVibe during a procedure requiring injections provides greater reduction in pain than injections with no intervention (standard of care). This information will aid healthcare providers in selecting the best approach to management of pain in patients who must undergo injections that could cause pain and may benefit from additional pain reduction.

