#### Targeted Medical History

Targeted medical history will be reviewed and recorded at Visit 1. Targeted medical history includes medical events associated with the use of NSAIDs, antiplatelets, anticoagulants, and analgesics.

Vital Signs (height, weight, & blood pressure)

Subjects will have their height, weight, and blood pressure obtained using calibrated, digital devices. Vital signs will be documented in the subject's source documents.

Fingersticks and Injections (Without Intervention/DigiVibe)

Subjects will first undergo a fingerstick with a 30-gauge Unistik lancing device on their middle finger with no intervention (as per standard of care). For the fingerstick, the targeted area of the middle finger will be disinfected with alcohol, the lancing device will be pressed firmly against the pulp of the middle finger, and the lancet will be activated.

Subjects will then undergo a SC injection with a 30-gauge 4mm needle on the lower quadrant of their abdomen at least 2 inches from the belly button with no intervention (as per standard of care). For the SC injection, 0.5 mL of NS will be drawn into the syringe, the needle will be replaced with a new 30-gauge 4mm needle, the targeted area of the lower abdomen will be disinfected with alcohol, the needle will be inserted at a 90-degree angle, the NS will be injected slowly but steadily, and the needle will be withdrawn quickly.

Subjects will then undergo an IM injection with either a 25-gauge 1 inch needle or a 30-gauge 1 inch needle in upper arm deltoid muscle with no intervention (as per standard of care). For the IM injection, 0.5 mL of NS will be drawn into the syringe, the needle will be replaced with a new 25-gauge 1 inch needle or 30-gauge 1 inch needle (depending on the subject's assignment (see above)), the targeted area of the upper arm deltoid muscle will be disinfected with alcohol, the needle will be inserted at a 90-degree angle, the NS will be injected slowly but steadily, and the needle will be withdrawn quickly.

Fingersticks and Injections (With DigiVibe)

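### Every subject has the no-intervention needle before the DigiVibe needle at all three sites, so the device effect cannot be separated from order and the superiority question cannot be answered

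*Combined protocol and SAP*

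**What the plan says.** Section 4.1 describes the design: "This is a single-center, unblinded, prospective, cross-over study". Section 4.2 gives the primary objective: "To demonstrate if the use of DigiVibe is superior to no intervention in reducing pain scores".

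Section 4.5 (Visit 1) sets the order for every subject:

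- Fingerstick: "The first fingerstick will be performed with no intervention (as per standard of care". Then: "After waiting 5 minutes, the DigiVibe device will be applied to the pulp of the other middle finger for 20 seconds", followed by the second fingerstick.
- SC injection: "The first SC injection will be performed with no intervention (as per standard of care". After 5 minutes the device goes on the other side of the abdomen and "then the second SC injection will be immediately performed with the DigiVibe device still vibrating the injection site".
- IM injection: "The first IM injection will be performed with no intervention (as per standard of care". The DigiVibe injection follows in the other deltoid after 5 minutes.

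The only assignment that varies between subjects is IM needle gauge, which alternates separately in men and women. Which body side goes first is not specified.

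Section 4.9.1 plans a paired t-test or Wilcoxon signed-rank test at each site, with no period or sequence term. No section states or justifies an assumption that order has no effect.

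Section 4.6 arranges the procedures differently. Under "Fingersticks and Injections (Without Intervention/DigiVibe" it runs through fingerstick, SC and IM without the device, and then gives all three with it. The schedule in 4.8 lists them in the same grouped way.

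**The concern.** A cross-over estimates a treatment effect free of order because some subjects receive the conditions in each order. Here there is a single sequence, so being the DigiVibe needle and being the second needle of its type are the same thing.

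An order effect is plausible in this study. Subjects are selected for fear or dislike of needles (4.3.2), the outcome is self-rated pain, and in 4.5 the second needle comes 5 minutes after the first. Relief of anticipation once the needle has been felt would lower the second score, and that fall would be credited to DigiVibe. Sensitisation would raise the second score and be charged against it. The documents do not show which of these would dominate.

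At stake is the meaning of the primary result: a significant p-value would not demonstrate superiority. Because the order is the same at all three sites, agreement between sites would not be independent corroboration. A secondary consequence, with no size attached, is that a subject who withdraws between the two needles of a pair always lacks the DigiVibe score and never the control score.

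**Working it through.** **Inputs from section 4.9.2:** n = 20; two-sided α = 0.05; mean paired difference 1.0 with SD of differences 1.5, or 0.75 with SD 1.0. **Assumption, not in the documents:** an order effect of 0 to 1.0 point on the 0–10 scale, in either direction.

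**1. The plan's own power.** For a paired t-test the noncentrality is (difference / SD) × √20 with 19 df.

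- 1.0 / 1.5 × √20 = 2.98, giving power 80.7% (plan: at least 80%).
- 0.75 / 1.0 × √20 = 3.35, giving power 88.9% (plan: at least 88%).

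Both stated figures reproduce. The fault is in the design, not in the power arithmetic.

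**2. What the paired difference estimates.** Let τ be the pain reduction due to DigiVibe and π the reduction from first to second needle for reasons of order. Let D = control score − DigiVibe score.

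- Control first: E(D) = τ + π.
- DigiVibe first: E(D) = τ − π.

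The plan contains only the first line: one equation in two unknowns. A design matrix with intercept, period and device has rank 2 of 3, so adding a period term to the planned data would not help. With both orders present the rank is 3 of 3: the average of the two sequence means is τ, and half their difference is π.

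**3. Inert device (τ = 0), pain lower at the second needle.** The formula of step 1 is used with π in place of the difference. The table shows the chance per site of significance in DigiVibe's favour.

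| Assumed π (points) | SD 1.5 | SD 1.0 |
|---|---|---|
| 0 | 2.5% | 2.5% |
| 0.25 | 10.5% | 18.5% |
| 0.5 | 29% | 56% |
| 0.75 | 56% | 89% |
| 1.0 | 81% | 99% |

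At π = 1.0 and SD 1.5 the inert device attains exactly the power planned for a real 1.0-point effect, because the two situations give the same data distribution.

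**4. Real benefit (τ = 1.0, SD 1.5), pain higher at the second needle.** The mean difference becomes 1.0 minus the rise.

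| Assumed rise (points) | Mean difference | Chance of detecting benefit |
|---|---|---|
| 0.25 | 0.75 | 56% |
| 0.5 | 0.50 | 29% |
| 0.75 | 0.25 | 10.5% |
| 1.0 | 0 | 2.5% |

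**5. Randomised order, 10:10, with a period term (18 df).** The estimate is the average of the two sequence means of D, with standard error s/√20.

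- Power is 80.5% (1.0, SD 1.5) and 88.7% (0.75, SD 1.0).
- Simulated two-sided type I error (100,000 trials, SD 1.5) is 5.0%, 5.0% and 5.1% for order effects of 0, 0.5 and 1.0 point. Under the plan's fixed order the same simulation gives 5.2%, 29.3% and 80.7%.
- If order is balanced but the unadjusted paired t-test is kept, the order effect inflates the SD to √(1.5² + π²). Power for a 1.0-point effect falls to about 77% at π = 0.5 and 65% at π = 1.0, so the period term is needed.

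**6. Position of the needles.** Under 4.5 each control needle is followed directly by its DigiVibe partner (positions 1–2, 3–4, 5–6). Read as a sequence, 4.6 and 4.8 put the control needles at 1, 2, 3 and the DigiVibe needles at 4, 5, 6. DigiVibe is second in its pair either way, but the interval and the intervening needles differ, so the order effect could differ too.

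**The case against.** The strongest reply is that the superiority question can be answered if the order effect is negligible, and nothing in the documents shows otherwise. Every inflation figure rests on an assumed order effect of unknown size and direction. This is true of the figures. But the plan neither states nor supports a zero order effect, and its own data could not test one, so the assumption would carry the whole conclusion.

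Several narrower points also have merit:

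- That the first needle carries the most anticipation is a reasonable expectation, not something the documents establish. Under 4.5 the first SC needle is already the subject's third needle and the first IM needle the fifth, so the order effect may vary by site.
- Side is unspecified rather than fixed, so no side confound is built in. Randomising side is good practice but secondary.
- No withdrawal rate is given and the visit is short, so the missing-pair point is minor.
- The schedule in 4.8 is a one-column checklist, and 4.6 still refers to the DigiVibe fingerstick as the second. The conflict with 4.5 may be one of presentation. It needs clarifying, but the main point does not depend on it.
- Randomising order does not remove bias from unblinded self-rating. That limitation remains after the fix.

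None of these separates device from order.

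**Conclusion.** The concern holds and must be fixed before enrolment, because order cannot be repaired after the data are collected. Device and order are completely confounded at all three sites. That follows from the design and needs no assumption about the size of the order effect. The bias in the primary estimate equals the whole order effect. Its effect on the test does depend on assumption: with an inert device, a 0.5-point fall at the second needle raises the chance of a false claim for DigiVibe at a site from 2.5% to 29% (SD 1.5) or 56% (SD 1.0). The direction is unknown, so it does not follow that the result will favour DigiVibe. As planned, the study supports a before/after description but not superiority.

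**What to change.** - **Randomise order.** Assign 10 subjects to control first and 10 to DigiVibe first, 5:5 within each sex, and randomise which body side goes first. Keep the 5-minute wait and the opposite-side site already planned. State whether one assignment governs all three procedures or each is randomised separately.
- **Keep order from aligning with needle gauge.** Gauge alternation within sex gives about 5 subjects per sex-by-gauge cell. Splits of 3:2 and 2:3 can be arranged so that order is 5:5 within each sex and within each gauge.
- **Amend section 4.9.1.** Analyse the within-subject difference with a sequence (period) term. As the rank-based alternative, compare second-minus-first differences between the two sequences with a Wilcoxon rank-sum test in place of the signed-rank test.
- **Reconcile the procedure sequence** in 4.5 with 4.6 and 4.8.
- **If the order cannot be changed,** describe the study as a single-sequence before/after comparison and remove the superiority objective.

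The cost is a randomisation list and a short amendment, with no added subjects, visits or needles. The period term uses one degree of freedom, so power at difference 1.0 and SD 1.5 goes from 80.7% to 80.5%. The downside is possible carryover when DigiVibe goes first, which the opposite-side site and the wait already limit. The report should still acknowledge the unblinded self-rating.

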Subjects will undergo a fingerstick with a 30-gauge Unistik lancing device on their middle finger using the DigiVibe device. For the fingerstick, the targeted area of the middle finger will be disinfected with alcohol, the DigiVibe device will be applied to the pulp of the middle finger for 20 seconds, the lancet device will be inserted into the center of the DigiVibe device, and then the second fingerstick will be immediately performed with the DigiVibe device still vibrating through the release of the lancing device.

Subjects will then undergo a SC injection with a 30-gauge 4mm needle on the lower quadrant of their abdomen at least 2 inches from the belly button using DigiVibe device. For the SC injection, 0.5 mL of NS will be drawn into the syringe, the needle will be replaced with a new 30-gauge 4mm needle, the targeted area of the lower abdomen will be disinfected with alcohol, the DigiVibe device will be applied to the abdomen on the lower quadrant for 20 seconds, the needle will be inserted at a 90-degree angle through the center of the DigiVibe device (with the DigiVibe device still vibrating), the NS will be injected slowly but steadily, and the needle will be withdrawn quickly. The DigiVibe device should continue vibrating on the injection site during the entire injection process until the needle is removed.

Subjects will then undergo an IM injection with either a 25-gauge or 30-gauge 1 inch needle (depending on their previous assignment) in the upper arm deltoid muscle using the DigiVibe device. For the IM injection, 0.5 mL of NS will be drawn into the syringe, the needle will be replaced with a new 25-gauge or 30-gauge (depending on their assignment) 1 inch needle, the targeted area of the upper arm deltoid muscle will be disinfected with alcohol, the DigiVibe device will be applied to the deltoid muscle for 20 seconds, the needle will be inserted at a 90-degree angle through the center of the DigiVibe device (with the DigiVibe device still vibrating), the NS will be injected slowly but steadily, and the needle will be withdrawn quickly. The DigiVibe device should continue vibrating on the injection site during the entire injection process until the needle is removed.

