## 4.9 Data Analysis

### 4.9.1 Statistical Analysis Plan

Demographics and baseline characteristics of study subjects will be summarized, as will VAS pain scores for the intervention (DigiVibe) and standard care. The primary analysis will be a paired t-test or Wilcoxon signed-rank test (depending on normality of VAS scores) to compare pain scores between standard care and DigiVibe. These tests will be performed individually for each of the injection sites (fingerstick, SC, IM).

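### The IM analysis omits needle gauge, a factor the trial assigns and records; including it costs almost nothing, protects precision and allows the device effect to be reported by gauge

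*Combined protocol and SAP*

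**What the plan says.** Section 4.5 (Visit 1) sets up two needle sizes for the IM site only: "Subjects will undergo alternating assignments to either a 25-gauge 1 inch needle or a 30-gauge 1 inch needle". It adds "The alternating assignment should be performed separately for the males and females so there is an equal distribution of males and females" across the two gauges, and "The alternating assignments must be documented". In Section 4.6, the account of the procedures with DigiVibe gives the second IM injection with "either a 25-gauge or 30-gauge 1 inch needle (depending on their previous assignment", so a subject's two IM injections use the same gauge. Section 4.1 plans "twenty (n=20) healthy subjects (10 men and 10 women". If all complete, that gives 5 per gauge in each sex and 10 per gauge overall.

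Gauge does not appear again. The endpoint in Section 4.2 is "Difference between DigiVibe and no intervention on pain scores". Section 4.9.1 says "The primary analysis will be a paired t-test or Wilcoxon signed-rank test (depending on normality of VAS scores" and "These tests will be performed individually for each of the injection sites (fingerstick, SC, IM". The power statement in Section 4.9.2 treats each site separately and does not mention gauge. No adjusted, stratified or descriptive result by gauge is planned.

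**The concern.** Gauge is the one factor that the trial assigns between subjects, and it is balanced and recorded. Because it is constant within a subject, its own effect on pain drops out of the paired difference. A difference between gauges in how much the device helps does not drop out. It spreads the 20 differences apart, and the pooled test counts that spread as error.

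Two things are at stake, both at the IM site only. The first is some avoidable loss of precision, if the device works differently with the two needles. The second is reporting: Section 4.1 says the results should help providers choose how to manage injection pain, but the planned IM result is one average over two needle sizes, with no prespecified estimate for either.

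**Working it through.** **Inputs.** From Section 4.9.2: n = 20, mean paired difference 1.0, SD of differences 1.5, two-sided alpha 0.05, and a second case of 0.75 with SD 1.0. From Sections 4.1 and 4.5: 10 subjects per gauge. Assumed, because the documents give no value: D, the difference between gauges in the device effect, from 0 to 2.0 VAS points. All 20 subjects are taken as evaluable.

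**1. The plan's own figures.** Noncentrality = (1.0/1.5) × √20 = 2.981. With 19 df, power is 80.7% (stated: at least 80%). For 0.75 and SD 1.0, power is 88.9% (stated: at least 88%). Both reproduce.

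**2. Cost of a gauge term when gauge does not matter.** The noncentrality is unchanged and the df fall from 19 to 18. Power is 80.5%, a loss of 0.2 points.

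**3. How D enters the pooled SD.** With 10 per gauge and within-gauge SD s, total SD = √(s² + (D²/4)(20/19)). For s = 1.5 and D = 1.0 this is √(2.25 + 0.263) = 1.585.

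**4. Power with and without gauge, mean effect 1.0.** Section 4.9.2 does not say whether 1.5 is the SD within a gauge or over all 20 IM differences, so both readings are shown. On the total-SD reading, s = √(2.25 − (D²/4)(20/19)), which is 1.410 at D = 1.0.

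- Planned pooled test: the scaled mean has noncentrality √20/s, and the sum of squares divided by s² is noncentral chi-square with 19 df and noncentrality 20(D/2)²/s². Power follows by numerical integration.
- Gauge in the model: noncentral t with 18 df and noncentrality √20/s.

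| Assumed D | 1.5 within gauge: planned | 1.5 within gauge: with gauge | 1.5 total: planned | 1.5 total: with gauge |
|---|---|---|---|---|
| 0 | 80.7% | 80.5% | 80.7% | 80.5% |
| 0.5 | 79.9% | 80.5% | 81.0% | 81.6% |
| 1.0 | 77.4% | 80.5% | 82.1% | 85.1% |
| 1.5 | 73.2% | 80.5% | 84.0% | 90.7% |
| 2.0 | 67.2% | 80.5% | 87.6% | 97.1% |

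Simulation of the planned test agrees to within about 0.2 points. In the second case (0.75, SD 1.0 within gauge), D = 1.0 gives 83.3% without gauge and 88.7% with it.

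**5. What results by gauge could show.** At within-gauge SD 1.5 and t(18) = 2.101:

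- device effect in one gauge, 95% CI half-width: 2.101 × 1.5/√10 = 1.00;
- difference between gauges: 2.101 × 1.5 × √(1/10 + 1/10) = 1.41.

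A test of the gauge difference would have about 29% power at D = 1.0 and would reach 80% only near D = 2.0. These are estimates to report, not powered comparisons.

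**The case against.** The planned test does what the objective asks. Section 4.2 compares DigiVibe with no intervention, and no objective, endpoint or hypothesis concerns gauge. A pooled paired test of 20 differences, balanced over two needles, estimates the average device effect without bias. All of that stands.

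The size of the gain also rests on an assumed D. At D = 1.0 the device effects would be 1.5 and 0.5, a difference as large as the planned effect itself. At D = 2.0 they would be 2.0 and zero. That also stands, so the upper rows of the table should not be read as likely.

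Three stronger readings are tempting, and the documents do not support them.

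- **That the stated power for IM is wrong.** This holds only if D is added on top of 1.5. Section 4.9.2 can as easily mean the SD of all IM differences, and then the planned test never falls below 80.7% over the range shown. Fitting gauge would still add power.
- **That the trial set out to compare gauges and then discarded the answer.** The protocol gives no purpose for using two needles. It explains only why the alternation is done within sex. Because the assignment is documented, a split by gauge stays possible; it is just not prespecified.
- **That alternation undermines the IM result.** Every subject receives both conditions with the same gauge, so a predictable gauge sequence cannot bias the device contrast. It limits only how a difference between gauges may be read.

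**Conclusion.** The point holds as one of efficiency and reporting, at one of three sites. The pooled IM test is valid and answers the stated objective. It leaves out a factor that the trial assigns, balances and records, and the plan gives no device effect by gauge.

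Fitting gauge costs at most 0.2 points of power in these calculations. It gains about 0.6 points at D = 0.5 and about 3 points at D = 1.0 on either reading of the SD. Those gains depend on an assumed D, on normal differences and on 10 evaluable subjects per gauge. The case for the change is that it is nearly free and prespecifies how gauge is handled, not that the present plan gives a wrong answer.

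**What to change.** Add to Section 4.9.1, for the IM site only:

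- **When the t-test branch applies:** fit a linear model to the paired differences with an intercept and gauge coded ±0.5. The intercept is the primary IM device effect, averaged equally over the two gauges.
- **When the Wilcoxon branch applies:** use a signed-rank or permutation test stratified by gauge.
- **In both branches:** report the device effect for each gauge and the difference between gauges, with 95% CIs, labelled exploratory. State that the gauge contrast comes from alternation, not randomisation.

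The cost is a few sentences in the analysis plan and one degree of freedom (80.7% to 80.5% power if gauge does not matter). No further subjects, visits or data are needed, because the gauge assignment is already recorded. The text should be settled before IM data are seen.
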